4.2.7. Exploratory Analyses of Special Interest

4.2.7.1. Relationship between onset of symptoms and viral load

It will be investigated if the onset of symptoms (ie., duration of RSV symptoms before treatment initiation) (days) is predictive of the treatment effect, or in other words if there is evidence of interaction between onset of symptoms and treatment effect.

To investigate this, the following outputs will be provided:

- A trellis plot of the log₁₀ RSV RNA viral load over time by treatment group and day of onset of symptoms showing the individual loads over time (spaghetti plots)
- A trellis plot of the average log₁₀ RSV RNA viral load over time by treatment group and day of onset of symptoms
- A trellis plot of the average log₁₀ RSV RNA viral load over time by treatment group and onset of symptoms ≤ 3 days and > 3 days (if this cut is sufficiently close to 50% - boundary may be adjusted)

If the data permit the primary endpoint will be fitted using the treatment group by day of onset of symptoms interaction term.

4.3. SAFETY

All safety analyses will be done on the Safety Set.

4.3.1. Adverse Events

The verbatim terms used in the eCRF by investigators to identify AEs will be coded using the Medical Dictionary for Regulatory Activities. Events are looked at on the level of their preferred term.

Definitions

Treatment-emergent AEs are AEs with onset during the treatment or the follow-up phase or that are a consequence of a pre-existing condition that has worsened since baseline. All reported treatment-emergent AEs will be included in the analysis. For each AE, the percentage of subjects who experience at least 1 occurrence of the given event will be summarized by treatment group.

Phase Allocation of AE

Step 1: Allocation of Events to the Phases

Adverse events present in the SDTM database are allocated to phases based on their start date. If the start date of an event falls between (or on) the start and stop date of a phase, the AE is attributed to that phase (treatment-emergent principle).

Incomplete dates (i.e. time and/or day and/or month and/or year missing):

- In case of partial start or stop dates, the events are allocated to the phases using the available partial information on start and end date; no imputation will be done. If, for instance, for the AE start date only month and year are available, these data are compared to the month and year information of the phases. This rule may lead to multiplication of the event as a consequence of its assignment to multiple phases.
- In case of a completely missing start date, the event is allocated to the first active treatment phase, except if the end date of the AE falls before the start of the first active treatment phase.
- In case of a completely missing end date, the following decision rules apply:
 - in case the date is identified as unknown the date will remain missing;
 - in case the date is not flagged as unknown the date is imputed by the cut-off date of the analysis for subjects still ongoing in the study, and by the end date of the last phase for subjects who discontinue.

Examples:

Screening phase: start date: 02JAN2017 - stop date: 28JAN2017

Treatment phase: start date: 29JAN2017 - stop date: 12AUG2017

1) Adverse event: start date: JAN2017- stop date: 15JUL2017

As the start date only has information about month and year, only this information will be used from the phases and therefore the AE will be assigned to the screening phase as well as to the treatment phase.

2) Adverse event: start date: JAN2017- stop date 27JAN2017 As the AE stops before or at the start of the treatment phase, it is only assigned to the Screening phase.

Remarks:

In addition to the date information, time information is taken into account to allocate AEs to phases.

Step 2: Combination of Events

Overlapping/consecutive events are defined as events of the same subject with the same preferred term who have at least 1 day overlap or for which the start date of an event is 1 day after the end date of the preceding event. Overlapping/consecutive events may be combined into one AE or not, according to the following rules:

- 1) In case a non-active phase (e.g. Screening) is followed by an active phase, and the overlapping/consecutive events start in both phases, they are allocated to their respective phase and are considered as separate events.
- 2) In case overlapping/consecutive events start within a single phase, they are considered as one and the same AE. The individual events who contribute to this AE are retained as individual records in the ADAM database but are assigned the same onset, phase, and total duration.
- 3) In case an active phase is followed by a non-active phase (e.g. Follow-Up), and the overlapping/consecutive events start in both phases, they are allocated to the active phase only and are considered as one and the same AE. The individual events who contribute to this AE are retained as individual records in the ADAM database but are assigned the same onset, treatment phase, and total duration.

Remarks:

- 1) Events can only be combined into one and the same AE if their start and stop dates are complete.
- 2) In case the completely missing end date is imputed, this date is also considered as a complete date.

- 3) Time is not considered when determining overlap of events.
- 4) Adverse events will be reported from the informed consent date on (i.e. in the screening period) until trial termination.

Analysis Methods

A Summary will be provided for the following treatment-emergent adverse events per phase (Treatment phase, Follow-up phase) and for the combination of Treatment and Follow-up phase: any adverse events, serious adverse events, deaths due to AE, adverse events by toxicity grade, AEs at least possibly related to study medication, AEs for which study medication was permanently stopped, serious adverse events that were at least possibly related to study medication. There will be no formal statistical testing.

Incidence tabulations will be provided for individual adverse events in the above categories (in case there are at least 5 events).

Listings will be provided for at least the following categories: all AEs, serious AEs, AEs leading to death, AEs leading to permanent stop, grade 3-4 AEs.

The summary, incidence tabulation for the individual preferred terms and subject listing will be provided for the RSV-related complications.

The following adverse events will be tabulated; or listed (in case there are less than 5 events) by subgroups (section 2.5): any AE, any RSV-related complications, any grade 1-2, any grade 3-4 AE, AEs that are at least possibly related to study medication, AEs leading to death, serious AEs, AEs leading to permanent stop of study medication.

4.3.2. Clinical Laboratory Tests

Laboratory parameters of hematology, serum chemistry and urinalysis will be investigated: All analyses will be done on SI-converted values as available in the database.

Unifying multiple laboratory values by standardization:

Since local labs are used, the SI-converted values will be standardized using the following formula and using the phantom laboratory generalized lab norms (GLN) as proposed by Francis Ruvuna, David Flores et al.^[13]

$$y = (x - Li) * \frac{Ucs - Lcs}{Ui - Li} + Lcs$$

Where

y = the transformed individual analyte value to a common standard laboratory reference range;

x = the original value;

L_i and U_i = lower and upper limits of normal for individual laboratory analyte;

L_{cs} and U_{cs} =lower and upper limit for the selected common standard laboratory or phantom laboratory GLN proposed by Francis Ruvana et all. [13]

The standardized values, with the phantom laboratory GLN will be used during the analysis.

Toxicity grades and abnormalities for laboratory parameters:

Toxicity grades will be computed according to the DMID adult toxicity grading list (see attachment at the end of this document). In case different grades are available for fasted/non fasted results, the results are assumed to be taken in the condition as specified in the protocol (i.e. not necessarily according to possible remarks indicating a deviation to this). If no condition is specified in the protocol, the non-fasting gradings should be used.

In case no toxicity grades are defined for any laboratory test, then non-graded abnormalities (high/low vs. normal range) will be used instead.

The worst grade over the whole observational period (treatment) will be determined.

Treatment-emergent definition for toxicity grades and abnormalities

An abnormality (toxicity grade or abnormality based on normal ranges) will be considered treatment-emergent in a particular phase if it is worse than the baseline value. If the baseline is missing, the abnormality is always considered as treatment-emergent. A shift from “abnormally low” at reference to “abnormally high” post reference (or vice versa) is also treatment-emergent. The treatment emergent definition is applicable in both, the treatment and follow-up phase.

Special assessments:

Additional laboratory assessments corresponding to the CRF rash-pages (if any and if applicable) will only be considered in the main analysis if they are provided by the same laboratory vendor as for the main, scheduled assessments.

Otherwise these assessments will only be listed; this also means that these assessments will not be considered in the determination of worst-case per treatment, but toxicity grades or non-graded abnormalities will anyways be determined as and if applicable.

In case of missing date or time parts:

Laboratory records with missing assessment date- or time-parts (any: day, month or year) will not be used in descriptive statistics, unless the scheduled target day or time is known and a unique phase allocation is possible taking this additional information into account. These assessments will be allocated to the correct phase using the available date(time) information, and the information on their assessment schedule. In case it is not possible to assign a unique phase (e.g. unscheduled time points), the assessment will be assigned to all possible active phases based on the available date and time information. These cases will be flagged in the respective listings.

Imputations of numerical values expressed as characters:

In case a laboratory test result is *censored* (no numeric value is available, but only a verbatim term), the following rules are applied:

- ‘<x’ or ‘>x’: a numeric value will be imputed by a value exceeding the cut-off value with one unit
- ‘≤x’ or ‘≥x’: imputation by x.

This also applies to normal limits expressed as such.

No such imputations will be done for urinalysis parameters as these are usually character/categorical expressions.

Missing normal limits:

Missing normal limits in the data base will be imputed at analysis level using the values specified and approved by the sponsor. This only applies if the missing normal limit is critical to determine a toxicity grade or an abnormality score, i.e. not for tests whose toxicity grade is based on the test value itself. Imputations, if applicable, will be flagged as applicable if shown in listings.

Derivation of GFR (CKD-EPI equation):

Estimated GFR (CKD-EPI equation) will be calculated using the following formula^[14]:

$$\text{GFR}(\text{mL}/\text{min}/1.73 \text{ m}^2) = 141 \times \text{minimum}(\text{CREAT} / \text{K} ; 1)^\alpha \times \text{maximum}(\text{CREAT} / \text{K} ; 1) \cdot 1.209 \times 0.993^{\text{Age}} \times (1.018 \text{ IF SEX} = \text{'F'}) \times (1.159 \text{ IF RACEGR1} = \text{'BLACK'})$$

Where:

CREAT= Serum Creatinine

Unit CREAT = mg/dL.

Conversion CREAT: mg/dL = $\mu\text{mol}/\text{L} / 88.4$

Unit WEIGHT = kg, unit HEIGHT = cm

Use last measurement before intake for weight and height (baseline).

Use age at screening.

$K = 0.7 \text{ IF SEX} = \text{'F'}$ or $0.9 \text{ IF SEX} = \text{'M'}$

$\alpha = -0.329 \text{ IF SEX} = \text{'F'}$ or $-0.411 \text{ IF SEX} = \text{'M'}$

With the following scores:

Grade 0: $\text{GFR} > 60 \text{ mL}/\text{min}/1.73\text{m}^2$ (grade 0);

Grade 1: $30 \text{ mL}/\text{min}/1.73\text{m}^2 < \text{GFR} \leq 60 \text{ mL}/\text{min}/1.73\text{m}^2$

Grade 2: $15 \text{ mL}/\text{min}/1.73\text{m}^2 < \text{GFR} \leq 30 \text{ mL}/\text{min}/1.73\text{m}^2$

Grade 3: $\text{GFR} \leq 15 \text{ mL}/\text{min}/1.73\text{m}^2$

Analysis Methods

Actual values and change from baseline will be summarized by treatment group at each scheduled time point.

The number and percentage of subjects will be shown in a cross-tabulation of the toxicity/abnormality post-baseline versus baseline at each scheduled time point.

Additionally, a cross-tabulation of the worst toxicity/abnormality versus baseline will be presented per phase (Treatment phase, Follow-up phase) and for the combination of Treatment and Follow-up phase. This table will also show the number and percentage of subjects per worst toxicity/abnormality, the number and percentage of subjects per treatment-emergent worst toxicity/abnormality and the cumulative number of subjects per treatment-emergent toxicity/abnormality or worse.

Mean \pm SE graphs over time for the actual values and changes from reference will be generated for all tests performed.

A listing of abnormal individual subject hematology and clinical chemistry values from scheduled and unscheduled time points will be provided. This listing will include all other time points for the corresponding subject/parameter.

Grade 2 or higher toxicity laboratory values will be listed separately.

Urinalysis results will be listed. Proteinuria and urine WBCs will be summarized.

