9.7. Safety Evaluations

Safety and tolerability will be evaluated throughout the study from signing of the ICF onwards until the last study-related activity (end of study/early withdrawal).

An IDMC will be established for this study to monitor the safety of subjects. Details regarding the IDMC are provided in Section [11.12](#).

Any clinically relevant changes occurring during the study must be recorded in the AE section of the eCRF.

Any clinically significant abnormalities persisting at the end of the study/early withdrawal will be followed by the investigator until resolution or until a clinically stable endpoint is reached.

Safety assessments will be based on medical review of AE reports and the results of vital sign measurements, ECGs, physical examinations, clinical laboratory tests, and other safety evaluations at specified time points as described in the [Time and Events Schedule](#).

In the event that an invasive procedure such as a blood draw, mid-turbinate nasal swab, vital signs assessments, and/or ECG are required at the same time, the order of completion should be ECG first, then vital signs/SpO₂, then mid-turbinate nasal swab, then blood draw, with the mid-turbinate nasal swab and blood draw being obtained as close to the scheduled time as possible.

Adverse Events

Adverse events will be reported by the subject or the subject's legally acceptable representative for the duration of the study. Adverse events will be followed by the investigator as specified in Section 12.

Clinical Laboratory Tests

Blood samples for serum chemistry and hematology will be collected and analyzed by a local laboratory. The investigator must review the laboratory results, document this review, and record any clinically relevant changes occurring during the study in the AE section of the eCRF. The laboratory reports must be filed with the source documents.

The following tests will be performed by a local laboratory as initiation of treatment is time-critical:

Hematology Panel

-hemoglobin	Percentage and absolute counts of:
-hematocrit	-basophils
-mean corpuscular hemoglobin	-eosinophils
-mean corpuscular hemoglobin concentration	-lymphocytes
-platelet count	-monocytes
-red cell distribution width	-neutrophils
-reticulocytes	
-RBC count	
-white blood cell (WBC) count	

Serum Chemistry Panel

-alkaline phosphatase	-creatinine
-ALT	-creatinine kinase
-AST	-glucose
-bicarbonate (optional)	-potassium
-blood urea nitrogen	-sodium

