9.9.4. Potential Risks

The nonclinical toxicity profile for ALS-008112 was similar to that previously observed for other marketed nucleoside analogs, where hematopoietic changes and genotoxicity were noted.

The toxicity profile established for ALS-008112 in nonclinical toxicology studies indicates a reversible and dose-related effect on the hematopoietic system where changes in bone marrow cytology were associated with changes in hematological parameters. Specifically, decreased circulating reticulocytes, changes in RBC-related parameters, and hypocellularity of erythroid cell lines in the bone marrow were observed, next to changes on white blood cells, mostly lymphocytes and neutrophils, along with changes in the bone marrow myeloid cells and lymphoid organs. Thrombocytopenia was seen in the dog at very high exposure.

As of 02 January 2018, in adult subjects hospitalized with RSV, 2 hematological serious/severe AEs have occurred and subsequently resolved. In these 2 cases (pancytopenia SAE in Study 64041575RSV2003; severe neutropenia in Study ALS-8176-510), the subject received ALS-008176, but both cases were confounded by multiple medical comorbidities and recent/concomitant use of multiple medications that have been reported to cause bone marrow toxicity. In addition, two Grade 4 SAEs of (febrile) neutropenia (laboratory Grade 4) considered possibly related to the study drug were reported in hospitalized pediatric subjects infected with RSV (1 subject in the MAD part of Study ALS-8176-503 and 1 subject in Study 64041575RSV2004).

Based on the available information, hematopoietic toxicity is considered a potential risk for ALS-008176 for adult and pediatric subjects, for which continued close monitoring of hematological parameters and clinical status in both RSV- and hMPV-infected and healthy subjects is warranted, as additional data are being collected in ongoing/future studies with ALS-008176. Importantly, these hematological side effects observed in both nonclinical and clinical studies with ALS-008176 were reversible.

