11.10. Safety Analyses

Safety data will be presented descriptively. No statistical testing of safety data is planned. For safety, baseline is defined as the last assessment prior to the first intake of study drug.

Adverse Events

The verbatim terms used in the eCRF by investigators to identify AEs will be coded using the Medical Dictionary for Regulatory Activities. Treatment-emergent AEs are AEs with onset during the treatment phase or that are a consequence of a preexisting condition that has worsened since baseline. All reported AEs will be included in the analysis. For each AE, the percentage of subjects who experience at least 1 occurrence of the given event will be summarized by treatment group. In addition, comparisons between treatment groups will be provided if appropriate.

Summaries, listings, datasets, or subject narratives may be provided, as appropriate, for those subjects who die, who discontinue treatment due to an AE, or who experience a severe AE or an SAE.

Clinical Laboratory Tests

Laboratory data will be summarized by type of laboratory test. Reference ranges and markedly abnormal results (specified in the SAP) will be used in the summary of laboratory data. Descriptive statistics will be calculated for each laboratory analyte at baseline and for observed values and changes from baseline at each scheduled time point. Changes from baseline results will be presented in pre- versus posttreatment cross-tabulations (with classes for below, within, and above normal ranges). Frequency tabulations of the abnormalities will be made. A listing of subjects with any laboratory results outside the reference ranges will be provided. A listing of subjects with any markedly abnormal laboratory results will also be provided.

The laboratory abnormalities will be determined according to the criteria specified in the draft Division of Microbiology and Infectious Diseases Adult Toxicity Table (see [Attachment 1](#)) and in accordance with the normal ranges of the clinical laboratory if no gradings are available.

Electrocardiogram

The effects on cardiovascular variables will be evaluated by means of descriptive statistics and frequency tabulations. These tables will include observed values and changes from baseline values at each scheduled time point (the predose ECG will be used as baseline). Frequency tabulations of the abnormalities will be made.

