ATTACHMENT

DMID ADULT TOXICITY GRADES FOR LABORATORY PARAMETERS

PARAMETER	Unit	GRADE 1	GRADE 2	GRADE 3	GRADE 4
Hemoglobin	g/dL	10.5 – 9.5	<9.5 – 8.0	<8.0 – 6.5	<6.5
Absolute Neutrophil Count	GIGA/L	1.50 – 1.00	<1.00 – 0.75	<0.75 – 0.50	<0.50
Platelets	GIGA/L	<100 – 75	<75 – 50	<50 – 20	<20
WBC, high	GIGA/L	11 – <13	13 – <15	15 – 30	>30
WBC, low	GIGA/L	1 – <4			<1
Fibrinogen, high	mg/dL	400 – 600	>600		
	µmol/L	11.76 – 17.65	>17.65		
Fibrinogen, low	mg/dL	200 – 100	<100 – 50	<50	
	µmol/L	5.88 – 2.94	<2.94 – 1.47	<1.47	
Prothrombin Time		>1.00 x ULN – 1.25 x ULN	>1.25 x ULN – 1.50 x ULN	>1.50 x ULN – 3.00 x ULN	>3.00 x ULN
Activated Partial Thromboplastin Time		>1.00 x ULN – 1.66 x ULN	>1.66 x ULN – 2.33 x ULN	>2.33 x ULN – 3.00 x ULN	>3.00 x ULN
AST		>1.0 x ULN – <2.0 x ULN	2.0 x ULN – <3.0 x ULN	3.0 x ULN – 8.0 x ULN	>8.0 x ULN
ALT		>1.0 x ULN – <2.0 x ULN	2.0 x ULN – <3.0 x ULN	3.0 x ULN – 8.0 x ULN	>8.0 x ULN
GGT		>1.0 x ULN – <2.0 x ULN	2.0 x ULN – <3.0 x ULN	3.0 x ULN – 8.0 x ULN	>8.0 x ULN
Alkaline Phosphatase		>1.0 x ULN – <2.0 x ULN	2.0 x ULN – <3.0 x ULN	3.0 x ULN – 8.0 x ULN	>8.0 x ULN
Amylase		>1.0 x ULN – 1.5 x ULN	>1.5 x ULN – 2.0 x ULN	>2.0 x ULN – 5.0 x ULN	>5.0 x ULN
Lipase		>1.0 x ULN – 1.5 x ULN	>1.5 x ULN – 2.0 x ULN	>2.0 x ULN – 5.0 x ULN	>5.0 x ULN
Hyponatremia	mEq/L mmol/L	135 – 130	<130 – 123	<123 – 116	<116
Hypernatremia	mEq/L mmol/L	146 – 150	>150 – 157	>157 – 165	>165
Hypokalemia	mEq/L mmol/L	3.4 – 3.0	<3.0 – 2.5	<2.5 – 2.0	<2.0
Hyperkalemia	mEq/L mmol/L	5.6 – 6.0	>6.0 – 6.5	>6.5 – 7.0	>7.0
Hypoalbuminemia	g/dL	<LLN – 3	<3 – 2	<2	
Hypoglycemia	mg/dL	64 – 55	<55 – 40	<40 – 30	<30
	mmol/L	3.55 – 3.05	<3.05 – 2.22	<2.22 – 1.67	<1.67
Hyperglycemia	mg/dL	116 – 160	>160 – 250	>250 – 500	>500
	mmol/L	6.44 – 8.88	>8.88 – 13.88	>13.88 – 27.75	>27.75
Hypocalcemia (corr. for albumin)	mg/dL	8.4 – 7.8	<7.8 – 7.0	<7.0 – 6.1	<6.1
	mmol/L	2.10 – 1.95	<1.95 – 1.75	<1.75 – 1.52	<1.52
Hypercalcemia (corr. for albumin)	mg/dL	10.6 – 11.5	>11.5 – 12.5	>12.5 – 13.5	>13.5
	mmol/L	2.64 – 2.87	>2.87 – 3.12	>3.12 – 3.37	>3.37
Hypomagnesemia	mEq/L	1.4 – 1.2	<1.2 – 0.9	<0.9 – 0.6	<0.6
	mmol/L	0.70 – 0.60	<0.60 – 0.45	<0.45 – 0.30	<0.30
Hypophosphatemia	mg/dL	2.4 – 2.0	<2.0 – 1.5	<1.5 – 1.0	<1.0
	mmol/L	0.77 – 0.65	<0.65 – 0.48	<0.48 – 0.32	<0.32
Hyperbilirubinemia (TB)		>1.0 x ULN – <1.5 x ULN	1.5 x ULN – <2.0 x ULN	2.0 x ULN – 3.0 x ULN	>3.0 x ULN

PARAMETER	Unit	GRADE 1	GRADE 2	GRADE 3	GRADE 4

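### SAP 4.3.2 does not exempt DMID toxicity grading from the linear rescaling of local laboratory values, so taken literally laboratory grades can come out too low or too high

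*SAP*

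**What the plan says.** Protocol 9.7 has the safety bloods run at the sites: "Blood samples for serum chemistry and hematology will be collected and analyzed by a local laboratory". SAP 4.3.2 opens with "All analyses will be done on SI-converted values as available in the database". It then adds: "Since local labs are used, the SI-converted values will be standardized using the following formula". The formula is a straight-line map from the local normal range to a common (phantom, GLN) range, and the paragraph ends "The standardized values, with the phantom laboratory GLN will be used during the analysis".

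Grading follows directly: "Toxicity grades will be computed according to the DMID adult toxicity grading list". Nothing says whether the graded value is the reported or the standardized one. Treatment-emergence, worst grade, the shift tables and a separate listing of Grade 2 or higher values all rest on that grade.

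Later in SAP 4.3.2, the rule for missing normal limits sets aside tests that are graded on the result itself. That remark concerns imputation of limits and is not stated as an exemption from rescaling.

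Protocol 11.10 grades by the DMID table and otherwise "in accordance with the normal ranges of the clinical laboratory if no gradings are available". It does not mention rescaling.

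**The concern.** The map preserves a result's position relative to the normal range. DMID grades mostly depend on something else. In the SAP attachment, haemoglobin, neutrophils and platelets have fixed cut-offs, and AST, ALT and creatinine have cut-offs in multiples of ULN. Severe cytopenias and large transaminase rises lie far outside the normal range, where a change of slope and intercept has most effect.

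These are the tests of most interest here. Protocol 9.9.4 states that "hematopoietic toxicity is considered a potential risk for ALS-008176" and describes two serious or severe haematological events in adults hospitalised with RSV. Amendment 4 added biochemistry samples in Part 2 to characterise the AST/ALT elevations seen in Part 1. With about 30 subjects per arm in Part 2, one misgraded subject moves a grade rate by about 3.3 percentage points (1/30).

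**Working it through.** The plan states no figure on this point, so there is nothing to reproduce. The check applies the SAP's formula to values near the grade boundaries.

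**Inputs from the SAP**
- Formula (SAP 4.3.2): y = (x − Li) × (Ucs − Lcs)/(Ui − Li) + Lcs, where Li and Ui are the local limits and Lcs and Ucs the common ones.
- Cut-offs (SAP attachment). Neutrophils (10⁹/L): Grade 1 1.50 to 1.00, Grade 2 below 1.00 to 0.75, Grade 3 below 0.75 to 0.50, Grade 4 below 0.50. Platelets (10⁹/L): Grade 2 below 75 to 50, Grade 3 below 50 to 20. Haemoglobin (g/dL): Grade 2 below 9.5 to 8.0, Grade 3 below 8.0 to 6.5. ALT: Grade 2 from 2.0 to below 3.0 x ULN, Grade 3 from 3.0 to 8.0 x ULN.

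**Inputs assumed**
- All local and common limits. Neither set is in the documents; the phantom norms are in a cited paper.
- A standardized ALT is compared with the common ULN.

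**Algebra**
- If the two ranges are equal, y = x. Otherwise the absolute value generally changes.
- Put x = k × Ui. Then y/Ucs = 1 + (k − 1) × (1 − Lcs/Ucs)/(1 − Li/Ui). For k other than 1 this equals k only if Li/Ui = Lcs/Ucs.
- x = Li gives y = Lcs and x = Ui gives y = Ucs, so below/within/above flags never change.

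**Numbers, moving down**
- Neutrophils 0.45, local 1.5–8.0, common 2.0–7.5: (0.45 − 1.5) × 5.5/6.5 + 2.0 = 1.11. Grade 4 becomes Grade 1.
- Same count, local 1.8–7.7: (0.45 − 1.8) × 5.5/5.9 + 2.0 = 0.74. Grade 4 becomes Grade 3.
- Platelets 45, local 130–400, common 150–400: (45 − 130) × 250/270 + 150 = 71. Grade 3 becomes Grade 2.
- Haemoglobin 7.8, local 11.5–15.5, common 12–16: (7.8 − 11.5) × 4/4 + 12 = 8.3. Grade 3 becomes Grade 2.
- ALT 3.0 x ULN, local 5–40, common 10–40: 1 + 2.0 × 0.75/0.875 = 2.71. Grade 3 becomes Grade 2.

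**Numbers, moving up**
- Neutrophils 0.90, local 2.0–7.0, common 1.5–8.0: (0.90 − 2.0) × 6.5/5.0 + 1.5 = 0.07. Grade 2 becomes Grade 4. With the same ranges, 0.40 becomes −0.58, an impossible count.
- ALT 2.9 x ULN, local 10–40, common 0–50: 1 + 1.9 × 1/0.75 = 3.53. Grade 2 becomes Grade 3.

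**Range of outcomes.** Neutrophil limits were varied over 1.4–2.2 (lower) and 6.3–8.0 (upper) for both the local and the common range, giving 2,916 combinations. A true 0.40 maps to between −1.50 and 1.58; it is downgraded in 43% of combinations and falls to Grade 2 or lower in 25%. A true 0.60 falls to Grade 2 or lower in 38% and rises to Grade 4 in 43%. These are shares of assumed range pairs, not expected patient rates.

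**The case against.** The SAP never says outright that grades are computed from standardized values, and two pieces of text favour the benign reading. The opening line of the section refers to SI-converted values. More tellingly, the missing-limits rule treats some tests as gradable from the result alone. If neutrophils were rescaled before grading, local limits would be needed for every neutrophil grade, and that rule would make little sense.

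This stands as evidence of what may have been intended, but it does not settle the matter. The SI-converted values are themselves the input to the standardization, so the opening line does not exclude it. The missing-limits remark has a different purpose. A programmer following the sentences in order would grade standardized values.

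Other limits also stand:
- A shifted value does not always change grade. ALT at 5.0 x ULN on the 5–40 to 10–40 ranges becomes 1 + 4.0 × 0.75/0.875 = 4.43 x and stays Grade 3.
- A reader might infer a conflict with the use of the clinical laboratory's own ranges in protocol 11.10. There is no numerical conflict, because high/low flags are unchanged by the map.
- Safety analyses are descriptive, so no formal test depends on the grades.

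**Conclusion.** The point holds as an ambiguity whose literal reading gives wrong laboratory grades, in both directions. The algebra needs no assumptions. Every numerical example rests on assumed ranges, and the documents do not allow the frequency or typical size of misgrading to be derived.

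The exposed outputs are the laboratory grade, shift and worst-grade tables, the Grade 2 or higher listing, and possibly eGFR, since SAP 4.3.2 does not say which creatinine value enters that formula.

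A reader might go further and infer that severe neutropenia would be hidden from the safety report. The documents do not support that. A count below the local lower limit remains below the common one, so the subject still qualifies for the abnormal-value listing, which shows that subject's other time points, and for the protocol 11.10 listing of results outside the reference ranges. Investigators review local results and record clinically relevant changes as adverse events (protocol 9.7). SAP 4.3.1 summarises adverse events by grade and lists Grades 3–4. Discontinuation under protocol 9.7.1 is decided at the site and does not pass through this rescaling. The remaining risk is that a subject's laboratory grade in the tables disagrees with the reported result.

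**What to change.** In SAP 4.3.2, before the tables are programmed:
- State that DMID grades are computed from the reported, SI-converted, unstandardized values and, for multiples of ULN, the originating laboratory's ULN.
- State that eGFR uses reported creatinine.
- Restrict GLN-standardized values to means, changes from baseline and plots over time.
- Reconcile the opening sentence on SI-converted values with the later one on standardized values.

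High/low flags need no change. The cost is a few sentences of SAP wording. No new data are needed, because the standardization formula already requires each reported value and its local limits. Grades are then correct whatever the local range: neutrophils 0.45 stay Grade 4 and ALT at 3.0 x local ULN stays Grade 3.
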